8.2 Comparability of Treatment Groups

To determine randomization effectiveness, differences in baseline demographic characteristics will be assessed between iCBT and self-monitoring groups using appropriate graphical and statistical methods including summary statistics. The randomization is designed to produce balance on important covariates. If we find imbalance on key covariates, we will consider adjusting for those covariates.

8.3 Analysis of Primary Outcome: HIV-Risk Behavior (Condomless Anal Sex)

Analysis	Primary analysis of primary outcome: Number of past-30-day condomless anal sex (CAS) acts with primary or casual partners as measured by the Timeline Follow-Back at the 8-month follow-up assessment.
Analysis population	All randomized participants
Endpoint	8-month follow-up
Unit of analysis	Participant
Method of analysis*	We will use repeated measures generalized linear mixed models with maximum likelihood estimation to test whether receipt of ESTEEM iCBT vs self-monitoring affects changes in the number of past-30-day CAS with primary or casual partners from baseline to 8-month follow up. We will use a contrast to test condition x time comparisons. We will test the best-fitting correlation structure, but based on our previous studies, expect it to be compound symmetrical. In the event of high skew or zero inflation, the appropriateness of modeling a negative binomial or Poisson distribution will be considered.
Handling of missing data	MAR assumption
Adjustment covariates	Adjustment for baseline covariates not balanced at randomization
Type I error	5% (2-sided)
Control of type I error	None

STATISTICAL ANALYSIS PLAN

Treatment effect estimate	Odds ratio with 95% confidence limits
---------------------------	---------------------------------------

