5.3 Eligibility Criteria

In order to be eligible for inclusion in Aim 2 of the study, an individual must meet all of the following criteria:

- 16-30 years old
- Live in Hunan province China
- Current gender identity as male
- Report past 12-month sex with men
- Be confirmed HIV-negative upon at-home testing
- Report past 3-month condomless/PrEP-less anal sex

- Past-week symptoms of depression or anxiety using the Brief Symptom Inventory-4 cutoff of 2.5 on either the depression subscale, anxiety subscale, or both
- No past 3-month mental health services of more than 2 visits per month
- Weekly access to internet on a laptop, desktop, or tablet device
- Ability to read, write, and speak in Mandarin
- Provision of informed consent

Any individual who meets any of the following criteria will be excluded from participation in this study:

- Current active suicidality or homicidality (defined as active intent or concrete plan, as opposed to passive ideation)
- Evidence of active and untreated mania or psychosis that could interfere with the participant's ability to volitionally consent to research or interfere with their ability to safely and reliably complete research

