7.2 Planned Analyses

Our primary hypothesis is that Chinese ESTEEM iCBT will yield significantly greater reductions in CAS and HIV risk behavior than weekly self-monitoring. Repeated measures intent-to-treat generalized linear mixed models (GLMM) with negative binomial distributions and maximum likelihood estimation will be fit to CAS at 4- and 8-month follow-up adjusted for baseline CAS with intervention arm as a covariate. We will test the best-fitting correlation structure, but based on our previous studies, expect it to be compound symmetrical. We will conduct exploratory analyses to determine within- and across-condition effects of each arm over time, including appropriate parameters for any trends evident over time. These models may be adjusted for any potential covariates (e.g., urban vs. rural residence; level of outness or education) that are associated with our outcomes if the intervention arms are not balanced on these variables.

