8.4 Analysis of Secondary Outcomes

A similar approach will be taken for our secondary outcomes (i.e., depression, anxiety, and minority stress variables) as described in Section 8.3.

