8.4.3.1 Moderation Analyses of Treatment Efficacy

Analysis	In these models, we will examine baseline depression (PHQ-9), anxiety (GAD-7), and minority stressors including concealment motivation (LGBIS), acceptance concerns (LGBIS), and internalized homonegativity (LGBIS) as potential moderators of
----------	---

STATISTICAL ANALYSIS PLAN

	ESTEEM iCBT efficacy, hypothesizing that YMSM with higher baseline depression, anxiety, and minority stress benefit most.
Analysis population	All participants
Endpoint	Immediate post-intervention (4-month follow-up) and 8-month follow-up
Unit of analysis	Participant
Method of analysis	
For all moderators (i.e., depression, anxiety, concealment motivation, acceptance concerns, and internalized homonegativity), a linear mixed model analysis will be performed. Moderation analysis models will include terms for condition, time, moderator, Condition X Time, Condition X Moderator, Time X Moderator, and Condition X Time X Moderator. To probe significant three-way interactions, we will perform simple slopes analyses and differences in slopes will be compared using z-score transformations.³⁵
 
We will test the best-fitting correlation structure, but based on our previous studies, expect it to be compound symmetrical. In the event of high skew or zero inflation, the appropriateness of modeling a negative binomial or Poisson distribution will be considered.

Handling of missing data	MAR assumption
Adjustment covariates	Adjustment for baseline covariates not balanced at randomization
Type I error	5% (2-sided)
Control of type I error	To control for the false discovery rate, we will apply a Bonferroni correction for each set of moderators (e.g., mental health, minority stress). Primary interpretation will focus on effect sizes.
Treatment effect estimate	Odds ratio with 95% confidence limits

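### SAP 8.3 does not carry over the protocol's adjustment for baseline CAS; if baseline arm means are left free, the 8-month contrast gives up precision that data already collected could recover

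*SAP*

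**What the plan says.** Protocol 7.2 plans repeated-measures negative binomial mixed models that "will be fit to CAS at 4- and 8-month follow-up adjusted for baseline CAS with intervention arm as a covariate". Baseline CAS is a covariate there, and only the two follow-up visits are outcomes.

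SAP 8.3 asks whether treatment "affects changes in the number of past-30-day CAS with primary or casual partners from baseline to 8-month follow up", and the SAP's Study Summary words the primary analysis the same way. The test is given as "We will use a contrast to test condition x time comparisons". The covariate row allows adjustment only for baseline covariates that turn out unbalanced, and the analysis population is "All randomized participants". Compound symmetry is expected, though the SAP will check which structure fits best. No model terms are listed. The method row carries an asterisk, but the note it points to is not in the text available.

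The only SAP model written out term by term is the one in 8.4.3.1: "Moderation analysis models will include terms for condition, time, moderator, Condition X Time". It has a condition main effect, so baseline arm means are free in that model. SAP 8.4 extends the primary approach: "A similar approach will be taken for our secondary outcomes".

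**The concern.** Randomisation makes the expected baseline means equal, so any baseline difference between arms is chance. A change contrast with free baseline means subtracts that difference in full. A baseline-adjusted contrast subtracts only the part that predicts the follow-up value. In the linear case the first is therefore never more precise than the second, and usually less.

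Two analysts could follow SAP 8.3 faithfully and fit models of different precision to the single primary endpoint. One of them would depart from the protocol without any stated reason. What is at stake is precision, not bias. In a trial of 120 the margin is thin, and the baseline values are already in hand.

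**Working it through.** **Inputs from the documents.** 60 per arm, 20% attrition (48 per arm at follow-up) and d = .40 (SAP 6.2); two-sided 5% and an 8-month endpoint (SAP 8.3).

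**Assumed, because the documents do not give them.** r, the correlation of baseline with 8-month CAS: .3, .5, .7. k, baseline SD divided by 8-month SD: 1 for the main figures, 0.5 to 1.5 as the range. d is in raw 8-month SDs. A linear model stands in for the count model.

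**The plan's own figure.** SAP 6.2 states at least 80% power. A plain two-sample t comparison with 48 per arm has noncentrality .40/√(2/48) = 1.96 and power 49%; with 60 per arm, 58%. The figure does not reproduce without help from repeated or baseline data, and no correlation is stated.

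**Variance of the 8-month arm effect (8-month SD = 1).**
- Baseline-adjusted: 2(1 − r²)/48.
- Free baseline, completers: 2(1 + k² − 2rk)/48 = 2[(1 − r²) + (k − r)²]/48.
- Free baseline, all randomised under maximum likelihood, with 12 per arm having baseline only (missing completely at random): 2[(1 − r²)/48 + (k − r)²/60].

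The excess is the (k − r)² term. It vanishes at k = r and is positive otherwise. Under a constant correlation, adding the 4-month visit does not alter the ratio.

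Worked at r = .5, k = 1: free 2(1)/48 = 0.0417; adjusted 2(.75)/48 = 0.0313; ratio 1.33. All randomised: 2(.75/48 + .25/60) = 0.0396; ratio 1.27.

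| k = 1 | r = .3 | r = .5 | r = .7 |
|---|---|---|---|
| Free, completers | 0.0583 | 0.0417 | 0.0250 |
| Free, all randomised | 0.0543 | 0.0396 | 0.0243 |
| Adjusted | 0.0379 | 0.0313 | 0.0213 |
| Ratio, completers | 1.54 | 1.33 | 1.18 |
| Ratio, all randomised | 1.43 | 1.27 | 1.14 |
| Power, free, completers | 37% | 49% | 71% |
| Power, free, all randomised | 40% | 51% | 72% |
| Power, adjusted | 53% | 61% | 78% |

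Power is from the noncentral t with 94 df (free) or 93 df (adjusted). To reach 80% at k = 1, r must be about .76 (free, completers) or .72 (adjusted).

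**Unequal spread.** Entry required participants to "Report past 3-month condomless/PrEP-less anal sex", so baseline and follow-up spread may differ. Completer ratios at r = .3/.5/.7 are 1.04/1.00/1.08 for k = 0.5 and 2.58/2.33/2.25 for k = 1.5.

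**Does the equal-baseline model always help?** Not if compound symmetry with one common variance is kept. Fitting that structure to data with unequal spread (three visits, 48 per arm), the variance ratio of free to equal-baseline is 0.91 and 0.83 at k = 0.5 with r = .5 and .7, and 0.94 at k = 0.75 with r = .7. Below 1, the equal-baseline model is the less precise one.

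**Counts.** A simulation of overdispersed counts (60 per arm, 10% lost before month 4 and 10% after, log link, exchangeable working correlation, 300 runs per setting) gave equal-baseline to free variance ratios of 0.60, 0.72 and 0.83 as the between-person share of variance rose. Inverted, these are 1.67, 1.38 and 1.21: same direction and similar size.

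**The case against.** The strongest reply is that SAP 8.3 never says baseline means are free. The inference comes from the term list of a different model, and the missing asterisk note may settle it. This stands: the documents show an unspecified primary model that does not match protocol 7.2, and the precision loss is conditional on how it is fitted.

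A second reply is that holding baseline means equal can itself lose precision under the compound symmetry the SAP expects. This also stands, as shown above, and it shapes the remedy. The never-less-precise result covers the baseline-covariate model, or an equal-baseline model with visit-specific variances, and no more.

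Third, a reader might infer that the variance could more than double. That needs k well above 1 on the raw scale, and it may not carry over to a log-link model, where variance is roughly 1/mean + dispersion. With an assumed mean falling from 4 to 2 and dispersion 1, raw variances are 4 + 16 = 20 and 2 + 4 = 6, so k = 1.83; log-scale variances are 1.25 and 1.5, so k = 0.91. The documents do not support a headline above 2.

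Fourth, the protocol's model names no arm-by-time term and may target an effect averaged over 4 and 8 months. So the comparator here, matched to the SAP's 8-month endpoint, is not clearly the protocol's own model.

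Finally, the unreproduced 80% is a separate matter. A reader might infer that baseline adjustment restores it; at k = 1 that holds only for r of about .72 or more.

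**Conclusion.** The point holds as a discrepancy between protocol and SAP with a likely, but not certain, cost in precision. Protocol 7.2 uses baseline CAS as an adjuster; SAP 8.3 neither does so nor says that the arms share a baseline mean. If baseline means are left free, the 8-month contrast has about 14% to 54% more variance at equal SDs and r from .3 to .7, depending on r and on whether baseline-only participants are counted. The loss is nil when k equals r, or if the unstated terms already deal with it. These sizes rest on assumed r and k and on a linear approximation, with a count simulation in agreement.

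Two stronger readings are not supported. The unadjusted contrast is not biased, since randomisation protects it. Nor do the documents show that the wording was changed after results were seen: the SAP was revised on 24 January 2023 and protocol 9.6 planned analysis from December 2022, but neither shows whether analysis had begun. The change should be made; confidence in its size is moderate.

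**What to change.** In SAP 8.3, list the model terms and reconcile them with protocol 7.2.

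- **Simplest:** model 4- and 8-month CAS with arm, time, arm by time and baseline CAS (for example log(baseline + 1)), with the 8-month arm contrast as primary. State that this drops participants with no follow-up, which departs from the stated population.
- **Alternative that keeps everyone randomised:** keep baseline as a repeated outcome with arm means held equal at baseline (time, plus arm by time at 4 and 8 months only). Require visit-specific variances, by an unstructured or heterogeneous covariance; do not use this form with homogeneous compound symmetry.

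Apply the same choice to the secondary outcomes in SAP 8.4.1 and 8.4.2 that have a usable baseline value. The HIV test result does not, since all participants are negative at entry. Leave the models in 8.4.3.1 outside this change where the moderator is the outcome's own baseline value; there "we will examine baseline depression (PHQ-9), anxiety (GAD-7), and minority stressors" as moderators.

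The cost is SAP wording and a dated reason, with no new data or participants. The record must state whether the change came before or after any unblinded analysis. If after, report the adjusted model as a sensitivity analysis.

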Minority stress underlies substantial mental health disparities affecting Chinese YMSM. Our research shows that stigma gives rise to minority stress reactions including chronic, anxious expectations of rejection; internalized homonegativity; and identity concealment.^{13,14,24,52,53} We estimate that 81% of YMSM in China conceal their sexual orientation from all or most others.⁴¹ Structural stigma in Chinese cultural norms lead a significant proportion of Chinese MSM to have sex with women.^{49,54,55} A meta-analysis showed that 26% of MSM had female sexual partners during the past 6 months and only

26% used condoms then.⁵⁶ An estimated 70% of MSM plan to eventually marry a woman.^{3,56} These identity-related stressors help explain Chinese YMSM's 2-6-times greater odds of depression, anxiety, and alcohol abuse compared to heterosexual men.^{12,24,27,43,57-61}

Minority stress and mental health problems drive Chinese YMSM's HIV risk. Minority stress and poor mental health are clear risks for Chinese YMSM's HIV transmission behaviors.^{12,26-31,50,52,62} Specifically, enacted and internalized stigma predict concealment,²⁴ which in turn predicts lack of HIV-preventative knowledge and behaviors.^{50,63} Minority stress is also associated with emotion dysregulation,⁶⁴⁻⁶⁶ hopelessness,⁶⁷⁻⁶⁹ impulsivity,⁷⁰ poor social support,^{26,71-73} and low self esteem,⁷³ which are also associated with HIV-risk behaviors.^{18,74,75} The mental health consequences of minority stress further predict HIV-risk behaviors: moderate depression is associated with MSM's condomless anal sex (CAS);^{32,76-78} anxiety increases avoiding coping and poor condom use communication;⁷⁹⁻⁸¹ and substance use encourages impulsive sexual behaviors.⁸²⁻⁸⁴

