6.2 Method of Assignment/Randomization (if applicable)

Participants who are confirmed eligible via the study screeners and who test negative for HIV based on the at home HIV/STI testing kit will then be randomized to ESTEEM iCBT or the weekly self-monitoring condition. Participant randomization will be stratified based on mental health (i.e., eligible based on depressive symptoms, anxiety symptoms, or both on the Brief Symptoms Inventory-4). Randomization will occur via use of a random number table generated by SPSS, which has been used reliably by [name] and her team successfully when implementing stratified randomization for previous studies.

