5. RANDOMIZATION

5.1 Method of Randomization

Randomization occurred on the participant level. Participants were randomly assigned to receive one of two conditions: iCBT ESTEEM or self-monitoring (N = 120). We used a 1:1 randomization scheme such that for every one participant randomized to iCBT ESTEEM, one participant was randomized to self-monitoring. Participant randomization was stratified based on mental health (i.e., eligible based on depressive symptoms, anxiety symptoms, or both based on the Brief Symptom Inventory-4). Stratified randomization occurred using a random number table generated by SPSS such that 60 participants were randomized to each condition.

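### No planned model includes the BSI-4 randomization stratum, and the imbalance rule is unlikely to add it; the cost is small and does not inflate type I error

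*SAP*

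**What the plan says.** **Design.** SAP 5.1: "Participant randomization was stratified based on mental health", in three levels by BSI-4 eligibility route. Protocol 6.2 says the same of the plan: "Participant randomization will be stratified based on mental health". Both name an SPSS random number table. SAP 5.1 adds a total of 60 per arm. Neither gives a block size or says how balance within strata is obtained.

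**Models.** Protocol 7.2 describes a model "fit to CAS at 4- and 8-month follow-up adjusted for baseline CAS with intervention arm as a covariate". SAP 8.3 instead tests a condition-by-time contrast on change from baseline to 8 months. SAP 8.4.1, 8.4.2.1 and 8.6 follow that form. SAP 8.4.3.1 adds baseline PHQ-9, GAD-7 or LGBIS moderators. The BSI-4 stratum appears in none of them.

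**Covariate rule.** There are three wordings:
- Protocol 7.2 allows, but does not require, adjustment for covariates that are "associated with our outcomes if the intervention arms are not balanced on these variables".
- SAP 8.2: "If we find imbalance on key covariates, we will consider adjusting for those covariates".
- SAP 8.3, repeated in 8.4.1, 8.4.2.1 and 8.4.3.1: "Adjustment for baseline covariates not balanced at randomization".

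None sets a threshold. The check described in SAP 8.2 is that "differences in baseline demographic characteristics will be assessed between iCBT and self-monitoring groups".

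**The concern.** An analysis should normally reflect the way patients were randomized. If allocation is balanced within strata and the stratum predicts the outcome, leaving it out puts stratum variance into the error term. The reported standard error is then too large and the test slightly conservative. If allocation is not balanced within strata, some true precision is lost instead.

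A stratum effect is plausible. Protocol 2.1 argues that "The mental health consequences of minority stress further predict HIV-risk behaviors", and the stratum uses the same constructs as the PHQ-9 and GAD-7 outcomes. It may still be modest, because everyone enrolled is symptomatic on at least one of the two.

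A rule triggered by imbalance is a poor way to bring in a stratification factor, because successful stratification removes the trigger. The three wordings also mean that two analysts following the plan could fit different primary models.

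**Working it through.** **Inputs.** From the documents: 60 per arm, 20% attrition (so 48 per arm, 96 in all), two-sided 5%, d = .40, three strata. Assumed, because the documents give no values: share of outcome variance explained by the stratum (R²), baseline correlation ρ, and stratum shares of .2/.2/.6.

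**The plan's own figure.** The plan gives none for the stratum. Its nearest figure is at least 80% power at d = .40. A plain two-sample calculation at 48 per arm gives 50%, and 80% is reached at 8 months with baseline as covariate only if ρ is about .72. That is a separate and larger matter, which adding the stratum does not repair.

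**Step 1: would the imbalance rule add the stratum?** The demographics listed in protocol 7.2.2 do not include the BSI-4 route (the full list is in a measures packet not available here). Had it been checked:
- permuted blocks of 4 within strata: flagged in 0 of 6,000 simulated trials;
- 60:60 with no balance within strata: flagged in about 5% at p < .05, or 55% if any level's standardized difference above 0.20 counts.

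**Step 2: baseline as covariate (protocol 7.2 form).** Take total variance 1 and the same stratum effect at both visits. Residual variance without the stratum is 1 − ρ². With it, the residual variance is (1 − R²) − (ρ − R²)²/(1 − R²). The ratio of standard errors is the square root of the first over the second. For ρ = .5:
- R² = .05: √(.75/.7368) = 1.009
- R² = .10: √(.75/.7222) = 1.019
- R² = .20: √(.75/.6875) = 1.044

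Over ρ from .3 to .7 the excess ranges from 0.5% to 7.5%. The implied type I error without the stratum at R² = .20 is 2(1 − Φ(1.96 × 1.044)) ≈ .041, which is below 5%.

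Simulation with 120 randomized, 20% lost at random, ρ = .5 and 8,000 trials per cell (Monte Carlo SE of type I error .002):

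| Assumed stratum R² | 5% | 10% | 20% |
|---|---|---|---|
| Balanced: excess in reported SE without stratum, net of 2 df | 0.6% | 1.6% | 4.1% |
| Balanced: type I error without stratum | .048 | .047 | .042 |
| Balanced: power gained at d = .40 by including it (points) | 0.1 | 1.1 | 3.1 |
| Not balanced: excess in true SE without stratum | −0.4% | 0.3% | 3.5% |
| Not balanced: power gained (points) | −0.3 | 0.4 | 3.0 |

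A negative binomial version (assumed dispersion 1, baseline mean 3, log baseline as covariate) gives 0.9% and 2.1% when balanced, and 0.0% and 1.3% when not, for assumed rate ratios of 1.5 and 2 between extreme strata.

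**Step 3: the SAP's own contrast.** With baseline as a repeated response, condition by time compares changes within person, so a stable stratum effect cancels. Simulated with three visits and compound symmetry, with against without stratum and stratum by time:
- R² constant at 10%: 0.0%
- R² constant at 20%: 0.3%
- R² falling 20%, 10%, 5% over the visits: 1.8%

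A separate run adding only a stratum main effect gave a mean SE ratio of 0.999.

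**Step 4: the open rule.** Protocol 7.2 names three example covariates. With three independent ones, a p < .05 trigger fires in 1 − .95³ = 14% of trials. Free choice between the adjusted and unadjusted result moved type I error from .049/.046/.051 to .051/.048/.053 at joint R² of 5/10/20%, about 0.2 percentage points.

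**The case against.** The strongest reply is that nothing of consequence follows for the primary test. The SAP's contrast is almost unaffected (0.0-0.3%), every R² is assumed, and at R² of 10% or less without balance within strata the gain is about nil. That stands, and it is why this is a minor point.

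A second reply is that SAP 8.2 speaks of key covariates, sets no threshold, and could admit the stratum. That stands in part. Under a loose standardized-difference rule and no balance within strata, the stratum would be flagged about half the time if anyone checked it. Hence the rule is unlikely, not unable, to add it.

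A reader might infer that omitting the stratum invalidates the test or inflates false positives. The documents do not support this; any error in the test is on the conservative side.

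A reader might also infer that the SAP must move to protocol 7.2's form to benefit. It need not, and a switch has its own cost: with baseline only as a covariate, a participant with no follow-up contributes nothing to the likelihood, while SAP 8.3 analyses everyone randomized.

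Nor does HIV-negative status at entry justify dropping baseline syphilis status. Syphilis is not an eligibility criterion in protocol 5.3, it is tested at baseline, and the SAP summary lists its result as change from baseline.

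**Conclusion.** The point holds and is minor. The stratum is absent from every planned model, and the imbalance-triggered row is unlikely to bring it in. Omission costs about 0.0-0.3% of the standard error under the SAP's contrast (1.8% if the stratum effect fades), and about 0.6/1.6/4.1% under protocol 7.2's form with balanced strata, ρ = .5 and R² of 5/10/20%. The larger figures should not be read as the effect on the SAP's primary analysis as written. All sizes rest on assumed R², ρ and stratum shares, and mostly on a linear approximation to a count outcome. The three wordings of the imbalance rule are mainly a transparency problem; in the case computed they add about 0.2 percentage points of type I error.

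**What to change.** - In the adjustment-covariates row of SAP 8.3, 8.4.1 and 8.4.2.1 (and so 8.6), write: *BSI-4 randomization stratum (three levels)*.
- If baseline stays a repeated response, as in the SAP now, include stratum and stratum by time. If the team uses protocol 7.2's form, include the stratum main effect with baseline as covariate. This change does not require moving from one form to the other.
- In 8.4.1, allow the stratum to be left out for HIV and syphilis test results if events are too few to fit it. Give no instruction to drop baseline syphilis status.
- End SAP 8.2 with: *Any adjustment prompted by observed imbalance is a sensitivity analysis and does not replace the primary result.* Make the row in 8.4.3.1 and the optional-adjustment sentence in protocol 7.2 match.

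**Cost.** A few lines of wording and 2 degrees of freedom. With stratum by time it is 2 + 2 = 4 for two visits or 2 + 4 = 6 for three. The stratum is an eligibility item, so it should be on record for everyone randomized. If it is unrelated to an outcome, the standard error rises by about 0.3% (balanced within strata) to 1.1% (not balanced), simulated for the 2-df form. For logit-link outcomes the odds ratio becomes conditional on stratum.
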